## **The Effect of Vitamin D and Exercise on Balance in Postmenopausal Women- NCT03608488**

**(07/01/2019)**

### **Protocol:**

In this study postmenopausal women aged 50 to 70 years were included. Participants who had vitamin D3 level below 10ng/dl randomized to 3 groups as following:

Group I- Vitamin D replacement (50.000 IU/per week, for 8 weeks)

Group II- Core and balance exercises for 8 weeks.

Group III- Vitamin D replacement (50.000 IU/per week, for 8 weeks) plus core and balance exercises

Participants with vitamin D3 level above 30ng/ml were designed as control group (group IV). Core and balance exercises were given them as well for 8 weeks.

Evaluations were performed at baseline and 8 weeks after treatment.

Berg balance scale, postural stability tests, fall risk assessments and Nottingham Health Profile were used.

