### **Statistical Analysis:**

The IBM SPSS Statistics 22 (SPSS IBM, Turkey) program was used for statistical analysis. The normality of the parameters was assessed with the Shapiro-Wilk test. Mean, median, standard deviation, and frequency was used as descriptive statistical methods. The Student's t-test and ANOVA were used to make comparisons between the parameters in each group that showed normal distribution. The Mann-Whitney U and Kruskal Wallis test was used to make comparisons between the parameters in each group that lacked normal distribution. The data were assessed at  $p <0.05$  significance level and 95% confidence interval.

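### The only group called control is a non-randomised, exercising group with higher vitamin D3, and the analysis names no randomised contrast, so efficacy could be judged against it

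*Combined protocol and SAP*

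**What the plan says.** The title announces "The Effect of Vitamin D and Exercise on Balance in Postmenopausal Women". Under Protocol, randomisation covers one population only: "Participants who had vitamin D3 level below 10ng/dl randomized to 3 groups as following". The three groups are vitamin D replacement (I), exercise (II) and both (III). Group II is described as "Group II- Core and balance exercises for 8 weeks".

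The fourth group has a different origin: "Participants with vitamin D3 level above 30ng/ml were designed as control group (group IV". No other group is called control. Its members are also treated: "Core and balance exercises were given them as well for 8 weeks".

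Outcomes are measured twice: "Evaluations were performed at baseline and 8 weeks after treatment".

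Under Statistical Analysis, "t-test and ANOVA were used to make comparisons between the parameters in each group that showed normal distribution", and "Mann-Whitney U and Kruskal Wallis test was used to make comparisons between the parameters in each group that lacked normal distribution". The section does not say which groups enter these tests, which pairs are compared, or whether follow-up levels or changes from baseline are analysed. It mentions no baseline adjustment and gives group IV no stated role.

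**The concern.** A group labelled control is normally the one against which treatment is judged. Here that label sits on the one group outside the randomisation, chosen because its vitamin D3 is high, and given the same exercise as group II. Women with vitamin D3 above 30 ng/ml may differ from deficient women in balance, general health and other ways before any treatment starts. A difference from group IV read as the effect of vitamin D or exercise could come wholly from those prior differences.

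The design does contain randomised comparisons that answer part of the title question. At stake is whether the conclusions come from those or from a confounded comparison, and the plan does not say.

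**Working it through.** **Step 1: what each pair of groups compares.** Four groups give 4 × 3 / 2 = 6 pairs. From the group definitions under Protocol:

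| Pair | Randomised? | What differs |
|---|---|---|
| III vs II | yes | vitamin D, on top of exercise |
| III vs I | yes | exercise, on top of vitamin D |
| I vs II | yes | vitamin D against exercise |
| I vs IV | no | population, vitamin D replacement and exercise |
| III vs IV | no | population and vitamin D replacement |
| II vs IV | no | population only |

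No pair that includes IV isolates a treatment, and II vs IV contains no treatment difference at all. This step needs no numbers. The Statistical Analysis section does not separate the first three rows from the last three.

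**Step 2: how large the distortion could be.** There is no plan figure to reproduce: the documents give no sample size, SD, population difference or correlation between visits. The following are assumptions: n = 15, 20 or 30 per group; unit SD at each visit; baseline-to-follow-up correlation ρ = 0.5, 0.7 or 0.8; IV shifted by δ = 0.5 SD at baseline (0.3 SD as a smaller case); no treatment effect; α = 0.05.

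*(a) Four-group ANOVA on follow-up levels, shift persists.* With one group of four shifted by δ, the noncentrality is λ = n[3(δ/4)² + (3δ/4)²] = 0.75nδ², with 3 and 4n − 4 df. For δ = 0.5, λ = 2.81, 3.75 and 5.63 at n = 15, 20 and 30, and the test is significant 24%, 32% and 48% of the time. For δ = 0.3 the rates are 11%, 14% and 19%. A direct two-group t-test against IV at δ = 0.5 gives similar rates: 26%, 34% and 48%.

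*(b) Four-group ANOVA on change scores.* If IV changes in parallel with the others, the shift cancels and the rate is about 5%. If instead women with equal baselines have equal expected follow-up, IV's shift at follow-up is ρδ and its mean change differs by −δ(1 − ρ) = −0.25, −0.15 or −0.10 SD. At n = 30 the test is then significant 14%, 10% or 8% of the time for ρ = 0.5, 0.7 or 0.8.

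*(c) Groups I–III only.* About 5%, because randomisation removes the population difference.

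**Step 3: whether using the baseline rescues the comparison with IV.** Differences are IV minus II, n = 30, ρ = 0.5 / 0.7 / 0.8, from simulation with 40,000 trials per setting:

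| True pattern | Change score: bias (SD); % significant | Baseline-adjusted: bias (SD); % significant |
|---|---|---|
| Parallel change | 0; 5% | 0.25 / 0.15 / 0.10; 18 / 12 / 9% |
| Equal follow-up at equal baseline | −0.25 / −0.15 / −0.10; 16 / 11 / 9% | 0; 5% |

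Each method is right under one pattern and biased by δ(1 − ρ) in size under the other. The baseline data alone cannot show which pattern holds, so neither method makes IV a safe comparator.

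**Step 4: what the baseline does within I–III.** Here its use affects precision only. ANCOVA reduces the variance of III vs II to about 76%, 52% or 37% of that for levels at n = 30, in line with 1 − ρ² = 0.75, 0.51 or 0.36.

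**The case against.** The strongest reply is that the plan nowhere says efficacy is judged against group IV. A reader might infer from the word control that it is, and that the trial's conclusions are therefore invalid. The documents do not support that. They show an unspecified analysis, not a demonstrated wrong one, and the harm is conditional on a use of IV that the text permits without stating. This stands.

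It also stands that the percentages depend on assumptions. A baseline was collected, so an analysis of change fits the text as well as an analysis of levels, and for change scores with parallel change the excess disappears. Nor does a significant four-group test say which groups differ; the pairwise rates are close, so this is a matter of precision in the illustration.

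Group IV may also be a reasonable reference for how women with higher vitamin D3 respond to the same exercise. That is granted. It is an observational question, and it does not make IV a control for either treatment.

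A reader might further infer that comparisons within I–III are biased because no baseline adjustment is listed. They are not: randomisation makes the unadjusted comparisons valid, and leaving out the baseline costs precision only.

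**Conclusion.** The concern holds in conditional form. The plan gives the label of control to a non-randomised, exercising group selected on vitamin D3, names none of the three randomised contrasts, and leaves open that efficacy is judged against that group. That no comparison with IV isolates a treatment follows from the group definitions and needs no assumption.

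The size of any resulting error does rest on assumptions. With no treatment effect, a 0.5 SD baseline shift and 15 to 30 per group, the four-group false-positive rate runs from about 5% to 24–48%, and the documents cannot say where in that range the trial lies.

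One related limit needs careful wording. A reader might infer that the effect of either treatment against no treatment cannot be estimated under any circumstances. With no randomised arm free of both treatments, that is so unless the two treatments are assumed not to interact; under that assumption III vs II and III vs I do estimate those effects. It should be corrected before efficacy conclusions are drawn, because the choice of comparator decides whether the title question gets a randomised or a confounded answer.

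**What to change.** 1. Base efficacy conclusions only on randomised groups I–III, and name the contrasts: III vs II (vitamin D added to exercise), III vs I (exercise added to vitamin D) and I vs II (head to head).
2. Adjust these contrasts for the baseline already collected, by ANCOVA, described as a gain in precision and not a correction of bias. Check normality on the model residuals and state the method for each measure, because an adjusted mean difference and a rank comparison estimate different things.
3. Rename IV a non-randomised comparison cohort (vitamin D3 above 30 ng/ml) and keep it out of the efficacy tests. Report IV minus II descriptively, as both the change-score and the baseline-adjusted difference with 95% confidence intervals. State that neither removes confounding and that the two can disagree when baselines differ.
4. State that no randomised arm goes without both treatments, so neither treatment's effect against no treatment can be estimated unless the two are assumed not to interact.
5. Label the contrasts post hoc if the data were already analysed, as the past tense of the Statistical Analysis section suggests they may have been.

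Testing the three pairs only after a significant overall I–III test is optional. Under no effect, the chance of at least one false-positive pair per measure is about 12% without that gate and about 5% with it. The gate does not control error across the several measures, and it can withhold a pairwise test.

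The cost is rewording and re-analysis of data already collected, with no new participants or measurements. The claim becomes narrower, IV's role becomes descriptive, and a post hoc label may be needed. Rewording cannot supply the missing arm without treatment, which remains a stated limitation.

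### The plan does not say whether follow-up values or changes are compared, and no named method uses the collected baseline as a covariate

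*Combined protocol and SAP*

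**What the plan says.** On measurement, the Protocol section says "Evaluations were performed at baseline and 8 weeks after treatment" and lists the instruments: "Berg balance scale, postural stability tests, fall risk assessments and Nottingham Health Profile were used". That is one baseline and one later value per outcome. The timing phrase could mean the end of the eight-week course or eight weeks beyond it, but there is one follow-up on either reading.

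On design, three groups are randomised ("Participants who had vitamin D3 level below 10ng/dl randomized to 3 groups as following"). Group IV is formed by having a high vitamin D level, not by randomisation.

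On analysis, the Statistical Analysis section gives two comparison rules, chosen by a Shapiro-Wilk test. For variables that pass it, the rule reads "The Student's t-test and ANOVA were used to make comparisons between the parameters in each group that showed normal distribution". For variables that fail it, rank tests for independent samples (Mann-Whitney U, Kruskal-Wallis) replace the parametric ones, with the same undefined term for what is compared.

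The section never defines what a parameter is (follow-up value, change or both). It names no ANCOVA, regression on baseline, repeated-measures or mixed model, and no paired test.

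**The concern.** Two separate things are at stake.

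**Precision.** Comparing follow-up values ignores baseline. Comparing changes, or using a group-by-time ANOVA, which with two visits gives the same test, fixes the baseline slope at 1. Neither estimates the slope from the data. For the randomised contrasts this gives wider intervals than the collected data could support, and estimates that depend more on chance differences at baseline.

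**An open choice.** Follow-up and change are different analyses of the same data. When the correlation lies between 0 and 1, a chance baseline gap pushes them in opposite directions. A plan that does not choose between them allows two results, and a reader cannot tell which was intended.

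**Working it through.** **Inputs.** From the documents: one baseline and one follow-up, three randomised groups, the four named tests, and a 0.05 significance level. Not in the documents, and therefore assumed: the baseline-to-follow-up correlation rho (0 to 0.8 or 0.9), equal SDs at both visits, normal data, a two-sided test, a pairwise comparison of two groups and, for simulation only, 20 per group. The plan states no power or sample size figure to reproduce.

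**Step 1: variance.** Taking the variance of a follow-up-only comparison as 1, change scores have 2(1 - rho) and ANCOVA has 1 - rho². Hence:
- ANCOVA / follow-up = 1 - rho²
- ANCOVA / change = (1 - rho²) / [2(1 - rho)] = (1 + rho)/2

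**Step 2: power and relative sample size.** Fix the effect at the size where ANCOVA has 80% power, so that effect/SE = 1.960 + 0.842 = 2.802. The power of another method is Phi(2.802 × √ratio - 1.960), and its relative sample size is 1/ratio. For example, follow-up-only at rho 0.8 has ratio 1 - 0.64 = 0.36, so power is Phi(2.802 × 0.6 - 1.960) = Phi(-0.279) = 39%, and relative N is 1/0.36 = 2.78.

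| rho | Follow-up: power | Follow-up: relative N | Change: power | Change: relative N |
|---|---|---|---|---|
| 0 | 80% | 1.00 | 51% | 2.00 |
| 0.3 | 76% | 1.10 | 62% | 1.54 |
| 0.5 | 68% | 1.33 | 68% | 1.33 |
| 0.7 | 52% | 1.96 | 73% | 1.18 |
| 0.8 | 39% | 2.78 | 76% | 1.11 |

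Follow-up values do badly when rho is high and change scores do badly when it is low; the crossover is at 0.5. As a cross-check, a direct sample-size calculation for an assumed difference of 0.5 SD at rho 0.5 gives 63 per group for follow-up, 63 for change and 48 for ANCOVA.

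**Step 3: effect of a chance baseline gap D.** Given D, the follow-up comparison shifts by rho × D and the change comparison by (rho - 1) × D. For D = 0.3 SD:

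| rho | Follow-up | Change |
|---|---|---|
| 0.3 | +0.09 SD | -0.21 SD |
| 0.5 | +0.15 SD | -0.15 SD |
| 0.8 | +0.24 SD | -0.06 SD |

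The two estimated mean differences always disagree by D itself: rho × D - (rho - 1) × D = D. With an assumed 20 per group, the standard error of a baseline difference is √(2/20) = 0.32 SD, so a gap of 0.3 SD would be ordinary.

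**Step 4: error rates.** In null simulations (20,000 trials per rho, 20 per group), follow-up, change and ANCOVA each rejected 4.6-5.1% of the time. Each is valid if fixed in advance. In a second null simulation (100,000 trials per rho, 20 per group), reporting the smaller p-value of follow-up and change gave 8.9% at rho 0.3, rising to 9.7% at rho 0.9, for one two-group comparison.

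**Step 5: price of the covariate.** At rho 0, where adjustment cannot help relative to follow-up values, simulated power was 76.5% for ANCOVA and 77.8% for follow-up-only, a loss of about 1 point.

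**The case against.** The strongest reply is that unadjusted comparisons of randomised groups are legitimate, so the absence of ANCOVA is a missed improvement and not an error. That stands for any metric fixed in advance. It does not cover the unfixed metric, for which the 5% rate no longer holds if the choice follows the results.

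Next, the sizes are not this trial's. They rest on assumed correlations, two groups, normal data and equal SDs. The 39% figure needs both a correlation of 0.8 and a follow-up-only analysis, and nothing was computed for the rank tests that the plan uses for non-normal outcomes. This also stands: the figures show direction and plausible range only.

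The wording about comparisons in each group might also be taken to mean before-and-after tests within groups. The named tests do not support that reading, since all four as named compare independent samples and no paired test is listed. If it were meant, the plan would state no between-group comparison of response at all.

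The scoring of the fall risk and postural stability measures is not given, and a categorical result would need a different model. This stands and limits the remedy to outcomes scored as continuous. Finally, the document is in the past tense, so pre-specification may no longer be possible. In that case the benefit is clear reporting and a labelled reanalysis.

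**Conclusion.** The concern holds. The text does not define the value compared, and no named method conditions on baseline. Confidence in that omission is high; the size of the consequence in this trial is unknown, because correlation, sample size, SD and effect are all unstated.

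Under the stated assumptions, the sample size needed relative to ANCOVA runs from 1.00 to 2.78 times for follow-up values and from 1.11 to 2.00 times for change scores, over correlations of 0 to 0.8. Apart from the degree of freedom it uses, ANCOVA is at least as precise as either across that range. The gain over follow-up values is small or nil when the correlation is near 0.

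This does not invalidate the comparisons among groups I to III. It also does not extend to group IV: that group was selected on vitamin D level, and baseline adjustment does not remove the selection difference.

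**What to change.** - State, for each outcome, which value is analysed.
- For outcomes scored as continuous, make the main analysis in groups I to III an ANCOVA of the follow-up value on randomised group and the baseline value of the same outcome, whatever the Shapiro-Wilk result.
- Report the adjusted differences III-II, III-I and I-II with 95% confidence intervals, and state that the target is the adjusted mean difference, which is not what the rank tests address.
- Use a rank-based or permutation analysis as sensitivity for skewed or bounded scales; robust standard errors are optional.
- Report group IV separately as a non-randomised comparison.
- If the data have already been analysed, say which metric was used and label the ANCOVA a post hoc reanalysis.

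The cost is revised wording, a little analysis work and one degree of freedom per model. No new data are required.

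### With no balance impairment required at entry and balance training in both arms, a cap on the Berg score could hide part or much of an added vitamin D benefit (group III versus II), and the plan makes no provision for it

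*Combined protocol and SAP*

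**What the plan says.** The Protocol section defines the population by menopausal status and age ("In this study postmenopausal women aged 50 to 70 years were included"). It admits women to the randomised groups by vitamin D level ("Participants who had vitamin D3 level below 10ng/dl randomized to 3 groups as following"). It states no balance impairment, fall history or limit on the baseline score.

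The comparator in the contrast of interest is exercise alone ("Group II- Core and balance exercises for 8 weeks"). Group III receives vitamin D "plus core and balance exercises". Four outcomes are listed and none is named primary: "Berg balance scale, postural stability tests, fall risk assessments and Nottingham Health Profile were used". On timing: "Evaluations were performed at baseline and 8 weeks after treatment".

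The Statistical Analysis section chooses tests by the Shapiro-Wilk result: "The Student's t-test and ANOVA were used to make comparisons between the parameters in each group that showed normal distribution"; and "The Mann-Whitney U and Kruskal Wallis test was used to make comparisons between the parameters in each group that lacked normal distribution". A 5% significance level and 95% confidence interval apply throughout. Neither section gives score ranges, baseline values, a sample size, adjustment for baseline, or any rule for scores at the limit of a scale.

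**The concern.** A summed score with a fixed best value cannot record improvement beyond that value. A woman at the cap at baseline can only stay or decline, and a woman near it can show only part of her gain. Because entry requires no balance problem, some women may start at or near the best Berg score, and the exercise given in both II and III would move more of them there. Any further effect of vitamin D then has less room to appear in III than the true effect would need.

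None of the named tests allows for this. The t-test and its confidence interval describe the shrunken difference. The rank tests treat everyone at the cap as tied. The plan gives a Berg result the same standing as the postural stability tests. A non-significant III-II Berg comparison could therefore be reported as vitamin D adding nothing to exercise when the scale had simply run out of range.

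**Working it through.** **No figure to reproduce.** The documents give no sample size, effect size, SD or score distribution, so what follows is a sensitivity calculation.

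**From the documents:** the arms, the absence of a balance criterion, the named tests and the 0.05 level (two-sided assumed).

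**Assumed:** the Berg total has a fixed best score; true balance at baseline is normal with mean 0 and SD 1; exercise adds 0.5 SD and vitamin D a further 0.5 SD, so the 8-week means are 0.5 (II) and 1.0 (III); the share at the cap at baseline is 10% to 60%. Power figures also assume 30 women per arm and, where baseline is used, a baseline-to-8-week correlation of 0.8.

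**Step 1: mean difference.** With cap c, set so that the chosen share lies above it at baseline, the mean observed score is

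E[min(X, c)] = μΦ(c − μ) − φ(c − μ) + c[1 − Φ(c − μ)].

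Example with 20% at the cap, c = 0.842:
- II: 0.5 × 0.634 − 0.376 + 0.842 × 0.366 = 0.249
- III: 1.0 × 0.437 − 0.394 + 0.842 × 0.563 = 0.517
- Difference: 0.517 − 0.249 = 0.268 SD, or 54% of 0.50.

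| At cap at baseline | II at cap, 8 weeks | III at cap, 8 weeks | III-II observed (true 0.50) | Retained |
|---|---|---|---|---|
| 10% | 22% | 39% | 0.35 | 70% |
| 20% | 37% | 56% | 0.27 | 54% |
| 40% | 60% | 77% | 0.16 | 31% |
| 60% | 77% | 89% | 0.08 | 16% |

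With 1% at the cap at baseline the same formula retains 94%.

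**Step 2: the same model, setting the cap by the share of group II at the best score at 8 weeks.** For a true III-II difference of 0.5 SD, the share retained is 85%, 72%, 61%, 40%, 22%, 14% and 6% when 10%, 20%, 30%, 50%, 70%, 80% and 90% of group II are capped. This agrees with Step 1: 22% of II capped gives 70% retained. With a true difference of 0.8 SD, 80%, 55%, 35% and 11% is retained at 10%, 30%, 50% and 80% capped.

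**Step 3: power of the named rank test.** Capping also shrinks the spread, so power falls less than the mean difference does. For Mann-Whitney on 8-week scores, power is 44% with no cap, then 40%, 31% and 25% with 20%, 40% and 60% capped at baseline (4,000 simulated trials per setting; repeat runs agreed within 2 points).

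**Step 4: baseline adjustment and the censored model.**

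| At cap at baseline | Linear, baseline-adjusted: estimate, power | Tobit: estimate, power | Whole-number scores: linear / Tobit power |
|---|---|---|---|
| 20% | 0.27, 70% | 0.49, 79% | 70% / 75% |
| 40% | 0.16, 50% | 0.49, 65% | 54% / 55% |
| 60% | 0.08, 30% | 0.51, 46% | 36% / 47% |

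(600 trials per setting; 300 for whole-number scores.) Baseline adjustment raises power over Mann-Whitney by 70 − 40 = 30, 50 − 31 = 19 and 30 − 25 = 5 points, but leaves the estimate shrunken. The censored model recovers the true size when the scale is continuous. With scores rounded down in 0.5 SD steps, its median estimates were 0.58, 0.61 and 0.67 against a truth of 0.50. Its large-sample test rejected in 6.8% of 400 null trials.

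**The case against.** The strongest objection is that the documents do not show a ceiling problem. They give neither the range of the Berg total nor any baseline scores. The absence of a balance criterion does not show that women start near the cap: the randomised women are deficient by the trial's own cut-off, and their balance is not reported. This stands, and it makes the point conditional.

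Four stronger readings are tempting, and the documents support none of them:

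- A reader might infer that the planned tests will hide most of the vitamin D benefit. That depends wholly on the unknown share at the cap. Heavily capped scores would also normally fail Shapiro-Wilk and go to Mann-Whitney, whose power falls only from 44% to 40% with 20% capped at baseline.
- A reader might infer a false impression that the two treatments overlap. Showing that needs the effect of vitamin D without exercise against no treatment. There is no untreated deficient arm, and no interaction test is planned.
- A reader might infer that a Tobit model must replace the named tests. Its recovery of the truth comes from data simulated under its own assumptions. It overshoots with coarse scores, and much of the power gain over Mann-Whitney comes from baseline adjustment alone.
- A reader might extend the figures to the Nottingham Health Profile. It may be affected in the same way, but no calculation was made for it, and nothing in the documents shows that balance exercise moves it to a limit.

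The postural stability tests and fall risk assessments are not shown to be capped, so a benefit could still appear there. That limits the damage. It does not stop a null Berg result from being misread.

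**Conclusion.** The point holds in conditional form. Capping can only shrink a true III-II difference on the Berg scale. Both arms train balance, no impairment is required at entry, and the Statistical Analysis section has no provision for the cap. Under the assumed 0.5 SD effects and a normal underlying scale, the loss of mean difference runs from negligible when few women are near the cap to 84% (100 − 16) with 60% capped at baseline. The loss of rank-test power is modest until capping is heavy.

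Because the share is unknown, the sensible course is to report it and to limit what a null Berg result may be said to show. This is a low-cost improvement to the plan. It is not evidence that the trial's Berg comparison fails.

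**What to change.** In the Statistical Analysis section, for the Berg scale in randomised groups I to III (and for the Nottingham Health Profile if its scores prove to be capped):

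1. Compare 8-week scores with adjustment for the baseline score.
2. Prespecify a proportional-odds or censored (Tobit) regression, with a bootstrap or permutation p-value, as a sensitivity analysis and not as a mandatory replacement.
3. Tabulate the number at the best score by arm at both visits.
4. Add a reading rule: if a prespecified share of either arm is at the best Berg score at 8 weeks, a non-significant III-II Berg difference is not reported as absence of a vitamin D effect, and that contrast is read alongside the postural stability tests. The share is a judgement. As a guide, Step 2 of the working retains 72% of a 0.5 SD difference with 20% of group II capped, and 40% with half capped.

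The cost is some SAP wording and a little more analysis, with no new visits or measurements. The downside is that the censored model assumes a roughly normal underlying scale, can overshoot with coarse scores, and may be slightly liberal in small arms; hence its secondary role and the resampling p-value. The plan is written in the past tense. If the data have already been analysed, these analyses should be labelled post hoc.
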